2.3 Secondary Laboratory Objectives

- 2.3.1 Association of inherited variation with immune mediated adverse events and response to ipilimumab + nivolumab
 - 2.3.1.1 To determine the association of inherited genetic variation and immune-associated adverse events in patients with metastatic melanoma treated with ipilimumab containing regimens by completing candidate-based gene and pathway analyses of genes involved in lymphocyte activation, cytokines, cytokine receptors and within the MHC region and an agnostic genome-wide SNP-based approach.
 - 2.3.1.2 To investigate the association between inherited genetics and survival in patients with metastatic melanoma treated

- with ipilimumab containing regimens by completing candidate-based gene and pathway analyses of genes involved in lymphocyte activation, cytokines profile, cytokine receptors and within the MHC region and an agnostic genome-wide SNP-based approach.
- 2.3.1.3 To replicate genomic markers identified in the above aims in an independent sample set of patients treated with ipilimumab containing regimens and preliminarily characterize their potential functional role by completing replication of variation as associated with irAEs and survival and bio-informatic assessment of genomic markers.
- 2.3.2 To determine the utility of circulating BRAF levels in determining the response and resistance to either BRAF/MEK directed and/or combination immunotherapy in patients with BRAF mutant melanoma.
- 2.3.2.1 To determine if changes in blood BRAF levels utilizing peripheral blood BRAF^{V600} mutational testing in patients with Stage IV BRAF mutant melanoma correlate with response and resistance to combination BRAF/MEK directed therapy.
- 2.3.2.2 To determine if changes in blood BRAF levels utilizing peripheral blood BRAF^{V600} mutational testing in patients with Stage IV BRAF mutant melanoma correlate with response and resistance to combination immunotherapy.
- 2.3.2.3 To compare the kinetics of peripheral blood BRAF^{V600} levels during response and resistance in groups of patients receiving BRAF targeted therapy or combination immunotherapy as initial therapy.
- 2.3.2.4 To compare the kinetics of peripheral blood BRAF^{V600} levels during response and resistance to combination BRAF targeted therapy or combination immunotherapy in individual patients (initial treatment vs crossover treatment).
- 2.4 Secondary Patient Reported Outcomes Objectives

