Analysis for survival outcomes will occur within the framework of Cox proportional hazards analysis, otherwise similar to analyses described above for irAEs. In addition to adjusting for age at diagnosis, sex, center, clinical trial and dose, adjustment for variables potentially associated with prognosis including AJCC stage, ulceration, performance status, lactate dehydrogenase (LDH) level, number of involved sites, BRAF/NRAS/WT tumor mutation status, and number of prior therapies will also be made.

Study Power: For replication phase irAE outcomes, the study has 80% power to detect a per-allele RR of 2.90 or greater for SNP markers with a MAF of at least 0.10. For analysis of 2 year survival, the study has 80% power to detect a per-allele HR of 1.83 or greater for SNP markers with a MAF of at least 0.10. These detectable measures of effect compare favorably to point estimates we found in our small preliminary study.

11.3 Evaluation of the Utility of Circulating BRAF Levels in Determining the Response and Resistance to Either BRAF Directed and/or Immunotherapy in Patients with BRAF Mutant Melanoma

11.3.1 Correlative Study Design:

To define the dynamic and kinetic effects of systemic therapy on peripheral blood BRAF^{V600} mutation detection, we will test isolated PBL and serum from samples obtained from patients prior to receiving treatment on each arm of the study. As part of trial eligibility, patients will have been previously identified as being positive for a BRAF^{V600} mutation based on the results of the testing of their tumor tissue (either primary tumor or nodal/systemic metastasis) in a CLIA-approved laboratory for BRAF^{V600} sequencing analysis. Heparinized blood will be collected on each patient at baseline and every 6 weeks on both initial and crossover therapy and at the time of both RECIST defined progression and crossover to the alternative therapy. Blood samples will be shipped overnight at room temperature to the ECOG-ACRIN melanoma immunotherapy laboratory at the Pittsburgh Cancer Institute for ficoll to isolate PBMC. Samples will be labeled and stored at minus 80 for batch analysis.

11.3.2 Specific Hypotheses:

- a) To determine if changes in blood BRAF levels utilizing peripheral blood BRAF^{V600} mutational testing in patients with Stage IV BRAF mutant melanoma correlate with response and resistance to combination BRAF/MEK directed therapy.

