dabrafenib/trametinib and 100 second-line dabrafenib/trametinib treated) will be included in this analysis. Of these, we hypothesize 50% will have a favorable outcome (CR+PR and their blood BRAF level will decrease at least by 50% from the baseline value. The change in blood BRAF level between week 12 and baseline will be compared among patients with favorable outcome vs. no favorable outcome (SD or PD). Two-sample t-test will be used to compare the changes in the blood BRAF levels among responders (n=125) and non-responders (n=125). If the standardized difference is 1.38, there will be 85% power. This is based on a two-sided type I error rate of 0.05. If the normality assumption is not appropriate, Wilcoxon rank-sum test will be used in the analysis.

For assessment of association with resistance, the change in blood BRAF level on the most recent test done prior to documentation of RECIST defined disease progression on CT scan relative to the nadir level will be used. It is expected that a total of 200 patients (125 first-line dabraf/tramet and 75 second-line dabraf/tramet treated) will be included in this analysis. Of these we hypothesize that pre-progression samples will show a 50% increase from the nadir sample. The changes from the nadir sample will be summarized using the descriptive statistics. Also the proportion of patients who had at least 50% increase will be summarized. With a sample size of 200, 95% confidence interval will not be wider than 14%.

Aim 2b: The change in blood BRAF levels between week 12 (after initiation of therapy) and baseline (before BRAF/MEK therapy begins) will be used. It is expected a total of 250 patients (150 first-line ipi/nivo and 100 second-line ipi/nivo treated) will be included in this analysis. Of these, we hypothesize 5% will have a favorable outcome (CR+PR) and their blood BRAF level will decrease at least by 50% from the baseline value. The change in blood BRAF level between week 12 and baseline will be compared among patients with favorable outcome vs. no favorable outcome (SD or PD). Two-sample t-test will be used to compare the changes in the blood BRAF levels among responders (n=135) and non-responders (n=115). If the standardized difference is 1.38, there will be 85% power. This is based on a two-sided type I error rate of 0.05. If the normality assumption is not appropriate, Wilcoxon rank-sum test will be used in the analysis.

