For assessment of association with resistance, the change in blood BRAF level on the most recent test done prior to documentation of RECIST defined disease progression on CT scan relative to the nadir level will be used. It is expected that a total of 200 patients (125 first-line dabraf/tramet and 75 second-line dabraf/tramet treated) will be included in this analysis. Of these we hypothesize that pre-progression samples will show a 50% increase from the nadir sample. The changes from the nadir sample will be summarized using the descriptive statistics. Also the proportion of patients who had at least 50% increase will be summarized. With a sample size of 200, 95% confidence interval will not be wider than 14%.

Aim 2c: Similar analyses as described under 2a/2b will be conducted in 150 patients with first-line therapy and 100 patients with second-line therapy in each group.

Aim 2d: The change in blood BRAF levels between week 12 and baseline will be compared between 150 patients receiving the first-line immune therapy vs. 150 patients receiving the first-line targeted therapy (at the time of response and progression as described in 2a/2b). A similar comparison will be made among 100 patients receiving second-line immune therapy vs. 100 patients receiving the second-line targeted therapy (at the time of response and progression as described in 2a/2b).

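### The BRAF resistance analysis (Section 11.3, Aims 2a and 2b) looks only at patients who progressed, each against their own nadir, so it has no comparator and cannot show association with resistance

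*Combined protocol and SAP*

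**What the plan says.** Objective 2.3.2.1 asks whether changes in blood BRAF level "correlate with response and resistance to combination BRAF/MEK directed therapy". Objective 2.3.2.2 asks the same for combination immunotherapy. Section 11.3.1 supplies the samples: "Heparinized blood will be collected on each patient at baseline and every 6 weeks on both initial and crossover therapy".

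The statistical text for Aim 2a introduces the resistance part as an assessment of association. The measure is the change on the "most recent test done prior to documentation of RECIST defined disease progression on CT scan relative to the nadir level will be used". The analysis set is given as follows: "It is expected that a total of 200 patients (125 first-line dabraf/tramet and 75 second-line dabraf/tramet treated) will be included in this analysis". The hypothesis is that "we hypothesize that pre-progression samples will show a 50% increase from the nadir sample". The analysis is descriptive statistics for the change, and then: "Also the proportion of patients who had at least 50% increase will be summarized". The only precision statement is "With a sample size of 200, 95% confidence interval will not be wider than 14" percent.

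Aim 2b concerns immunotherapy, but it repeats this paragraph word for word, including the dabrafenib/trametinib patient counts. Aim 2c refers to "150 patients with first-line therapy and 100 patients with second-line therapy in each group", and Aims 2c and 2d compare therapies or lines of therapy.

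**The concern.** Association with resistance needs a contrast: levels in patients about to progress against levels in patients who are not. The measure requires a progression date, so everyone in the set of 200 is a progressor and there is nobody to compare them with. The response half of the same aim does have two groups, since it compares responders with non-responders by a two-sample t-test.

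The choice of reference adds a second difficulty. The lowest of several noisy readings tends to lie below the patient's true level, so a later reading tends to exceed it even when nothing has changed. The more samples a patient has, the lower that minimum is likely to be.

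The resistance half of objectives 2.3.2.1 and 2.3.2.2 is at stake. A high proportion with a 50% rise would invite the reading that BRAF gives warning of progression, and the planned analysis has nothing to set that proportion against.

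**Working it through.** **Inputs.** 200 progressors (125 + 75) and 250 treated patients per regimen (150 + 100), from Section 11.3. Sampling every 6 weeks, from Section 11.3.1. Median PFS of 9.4 months on dabrafenib + trametinib, from Section 1.8; this is about 41 weeks, so about 6 on-treatment samples (41/6 = 6.8). Imaging every 12 weeks, from Sections 6.1 and 7.1.1, so a patient progressing at the first scan has about 2. Within-patient CV: not in the supplied text, so taken over a range.

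**Step 1: the plan's own figure.** The full Wald width at p = 0.5 and n = 200 is 2 × 1.96 × √(0.25/200) = 13.9%, which reproduces the stated 14%. The Wilson width is 13.7% and the exact width 14.3%. The arithmetic is sound; the difficulty is what the interval describes.

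**Step 2: who contributes.**

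| Part of the aim | Groups | Method |
|---|---|---|
| Response | Responders and non-responders | Two-sample t-test |
| Resistance | Progressors only | Descriptive; one proportion with CI |
| Aims 2c, 2d | Therapies or lines of therapy | As in 2a/2b |

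No row compares progressors with progression-free patients, and no reference rate under no association is given. This step needs no assumption about the assay.

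**Step 3: what noise alone gives.** Suppose the true level is constant and a patient has k on-treatment samples with independent lognormal variation, where SD on the log scale = √(ln(1 + CV²)). The share of patients with last/minimum ≥ 1.5, from 400,000 simulated patients per cell, is:

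| CV (assumed) | k = 2 | k = 4 | k = 6 | k = 9 | k = 12 |
|---|---|---|---|---|---|
| 10% | 0.2% | 0.6% | 0.9% | 1.3% | 1.7% |
| 20% | 7.4% | 16.7% | 22.9% | 29.4% | 34.2% |
| 30% | 16.4% | 33.1% | 42.5% | 51.0% | 56.7% |
| 50% | 27.1% | 49.4% | 59.6% | 68.3% | 73.5% |

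The k = 2 column can be checked by hand as 1 − Φ(ln 1.5 / (SD × √2)). At CV 20%, SD = 0.198, so 1 − Φ(0.405/0.280) = 1 − Φ(1.45) = 7.4%.

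The same formula gives the rate for a single fixed reference in place of the minimum: 16% at CV 30% and 27% at CV 50%. At six samples, the increase from 16% to 42.5% (CV 30%) or from 27% to 60% (CV 50%) therefore comes from choosing the minimum.

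The median noise-only rise at six samples is 12% at CV 10%, 26% at 20%, 40% at 30%, 56% at 40% and 72% at 50%. It passes the hypothesised 50% at a CV between 30% and 40%.

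**Step 4: is a comparator available?** 250 − 200 = 50 patients per regimen fall outside the resistance set. For illustration only, suppose 50% of progressors and 30% of these 50 met the rule. The standard error of the difference is √(0.25/200 + 0.21/50) = 0.074, so the 95% CI is about ±14.5 percentage points, and power at two-sided 0.05 is 73%. At 50% against 25%, power is 91%. The documents give no such proportions. Patients who progress later also serve as comparators while still progression-free, so the pool at early sample numbers is larger than 50.

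**The case against.** The strongest reply is that the plan claims little here. It specifies descriptive statistics and an interval, with no test and no statement about early warning. The measure follows from the preliminary data in Section 11.3.3, where levels fell on treatment and rose at or before radiographic progression. A flat series is a deliberately pessimistic null. Samples are stored for batch analysis and a standard curve is run with each batch, which may limit run-to-run variation. Part of Section 11.3, between the assay background and the statistical text, is not in the material supplied and may contain repeatability data.

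Much of this stands against the noise argument. The absence of a CV cannot be held against the plan, and at CV 10% the artefact is negligible. Six samples is typical only for patients near the median PFS; those who progress at the first scan have about two, and their rate is much lower.

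It does not answer the missing comparator. The text itself calls this an assessment of association, and the resistance paragraph is complete as supplied. The preliminary data as supplied give no rate of rise in patients still progression-free, so they motivate a controlled comparison without replacing it.

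A reader might go further and infer that ordinary assay variation would produce a figure such as 60%, or that the ratio to nadir is at least 1 by construction. The documents support neither. The first needs a CV of about 50% with six samples, and nothing shows that this is ordinary for this assay. The second depends on whether the nadir may include the last sample, which is not stated; if it is the lowest earlier value, the ratio can fall below 1. The proportions in the table are the same under either definition.

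**Conclusion.** The concern holds in two parts of different strength.

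The structural part is unconditional. As written, the analysis cannot answer the resistance half of objectives 2.3.2.1 and 2.3.2.2, because it contains no patients without progression. For 2.3.2.2 there is a further and more direct obstacle: the Aim 2b paragraph describes dabrafenib/trametinib patients where ipilimumab/nivolumab patients are needed.

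The noise part is conditional on the assay. At six samples the noise-only rate runs from about 1% (CV 10%) to 60% (CV 50%), and it becomes material from a CV of about 20%. These figures assume a constant true level and independent variation between samples. They show that the planned proportion is uninterpretable without a reference rate. They do not show that any observed rise would be an artefact.

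This is a secondary laboratory objective, so the consequence is limited to what can be concluded about BRAF as a marker of resistance.

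**What to change.** - Apply the same last-versus-nadir definition to patients on the same regimen who are still progression-free at the same sample number. Matching on sample number matters because the noise-only rate rises with k.
- Report the proportion with a rise of at least 50% in each group, and the difference with its 95% CI. If a patient can serve as comparator more than once, the interval should allow for that.
- An acceptable alternative is a time-to-progression model with log(current level/nadir to date) as a lagged time-dependent covariate.
- State whether the nadir may include the last sample.
- Keep the progressor-only proportion, labelled as description.
- Correct the Aim 2b resistance paragraph so that it refers to ipilimumab/nivolumab-treated patients, with their own expected numbers.

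The cost is small. The 6-weekly samples are already collected from consenting patients, so no extra blood or patients are needed. The comparator samples must be included in the batch assay, and programming is slightly heavier. The primary endpoint is not touched.

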Fig 5. Incidence of grade 3-4 AEs. From Sznol et al: "Pooled Analysis Safety Profile of Nivolumab and Ipilimumab Combination Therapy" (5). The percent of patients who experienced at least one grade 3-4 irAE at the respective times (total n=448) are shown [from the original Figure in Ref. (5)]. **Arrows:** time points of **blood collection** in the current study.

Statistical Design and Analysis Plan

Sample Availability Assessed as of July 2020

Overall 90% of the patients consented to participate in the correlative study. We summarized inventory for patients enrolled as of 12/31/19 (as our assessment requires at least 24 weeks of follow-up time) and projected the numbers for the remaining patients.

Aim 1a: Based on the data as of 12/31/19, 90% of the enrolled patients consented to participate in the correlative study. Of the consented patients, 90% had baseline samples and 86% (of the cases submitted baseline samples) had samples on at least one FU time point. At the completion of the study, approximately 104 patients (150X.9X.86) will provide samples for the analysis proposed in Aim 1a. The crossover rate (to arm C or D) was lower than anticipated, but could not be assessed accurately at this point as the study is still being conducted. We project at least 46 patients crossed over to arm D will provide samples for Aim 1a. Therefore, the overall sample size for Aim 1a will be approximately 150 patients.

Aims 1b and 2: As of 12/31/19, approximately 50% of the patients in arm A or D had grade 3 or higher irAEs and submitted samples. Therefore, we project approximately 75 patients will have consented and submitted irAE samples when accrual is completed. The remainder of subjects with less toxicity (~75) will serve as controls.

Study Design and Analysis

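### Section 11.3 sizes the ipi/nivo circulating-BRAF analysis (Aim 2b) on all 250 patients expected to be treated, but Appendix XVI projects samples from about 150 to 200

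*Combined protocol and SAP*

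**What the plan says.** Section 11.3, Aim 2b, compares the baseline-to-week-12 change in blood BRAF between responders and non-responders to ipi/nivo. On the number of patients it says: "It is expected a total of 250 patients (150 first-line ipi/nivo and 100 second-line ipi/nivo treated) will be included in this analysis". These are split 135 responders to 115 non-responders. The parallel dabrafenib/trametinib analysis (Aim 2a) is split 125 to 125. For both, the plan states "If the standardized difference is 1.38, there will be 85% power", and adds "This is based on a two-sided type I error rate of 0.05". Aims 2c and 2d reuse 150 first-line and 100 second-line patients per regimen.

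The resistance analyses rest on 200 dabrafenib/trametinib patients (125 first-line, 75 second-line): "With a sample size of 200, 95% confidence interval will not be wider than 14" per cent.

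Section 10 makes research blood conditional on patient consent. Appendix XVI holds two later projections, both dated July 2020:

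- Under the number of subjects, it expects 150 patients to receive ipi/nivo on Arm A and 100 on Arm D, and projects that 75% to 80% of subjects will have consented and submitted serum.
- Under sample availability, it reports 90% consent, baseline samples in 90% of consenters, and at least one follow-up sample in 86% of those. It adds that "The crossover rate (to arm C or D) was lower than anticipated", though this could not yet be measured accurately. It projects about 104 first-line patients and at least 46 on Arm D, and concludes: "Therefore, the overall sample size for Aim 1a will be approximately 150 patients".

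**The concern.** The 250 in Aim 2b equals everyone expected to be treated with ipi/nivo. It can be reached only if every treated patient consents, gives a baseline and a week-12 sample, and 100 patients cross over to Arm D. The same protocol later reports losses at each of those steps and updates the sample size for the Appendix XVI aims, but not for Section 11.3. The current text therefore carries incompatible sample yields for the same two arms.

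Circulating BRAF is a listed secondary laboratory objective (2.3.2). A reader judging a null or imprecise result would use the count, power and interval width printed in 11.3. If the count is too high, and the effect size beside it does not match the power, that reader cannot tell what the analysis was able to detect.

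**Working it through.** **1. Patients with samples, ipi/nivo (Arms A and D).**

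- Section 11.3: 150 + 100 = 250.
- Appendix XVI, sample availability: 150 × 0.9 × 0.9 × 0.86 = 104.5 first-line. Adding at least 46 gives about 150, or 60% of 250.
- The product printed there, 150 × 0.9 × 0.86, is 116.1. The figure of 104 needs the second factor of 0.9 (baseline sample among consenters).
- Appendix XVI, number of subjects: 250 × 0.75 = 187.5 and 250 × 0.80 = 200.

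The 86% counts any follow-up sample, not the week-12 sample that Aim 2b needs, so the usable number could be lower than these.

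**2. The plan's own power.** For a two-sample t-test at two-sided 0.05, the noncentrality is λ = d × √(n₁n₂/(n₁+n₂)), and power is roughly Φ(λ − 1.96). The percentages below use the noncentral t distribution.

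- d = 1.38, 125/125: λ = 1.38 × √62.5 = 10.9, power above 99.9%. The printed 85% does not reproduce. At d = 1.38, 85% power needs only 10 to 11 patients per group.
- d = 0.38, 125/125: λ = 0.38 × √62.5 = 3.00, power 84.9%. At 135/115 it is 84.7%. The stated 85% therefore corresponds to a difference of about 0.38, a value the documents do not print.

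**3. Power at the projected counts.**

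| Patients (split) | Power at d = 1.38 | Power at d = 0.38 | d detectable with 85% power |
|---|---|---|---|
| 250 (125/125) | >99.9% | 84.9% | 0.38 |
| 200 (100/100) | >99.9% | 76.2% | 0.43 |
| 188 (94/94) | >99.9% | 73.6% | 0.44 |
| 150 (75/75) | >99.9% | 63.8% | 0.49 |
| 150 (81/69) | >99.9% | 63.5% | 0.49 |
| 150 (90/60) | >99.9% | 62.0% | 0.50 |

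The 81/69 split keeps the plan's 135:115 ratio. The 90/60 split uses the 60% response that Appendix XVI assumes.

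**4. Interval width for the resistance analyses.** The worst-case width is 2 × 1.96 × √(0.25/n). At n = 200 this is 13.9%, so the plan's figure reproduces. A width of 14.0% needs n of at least 196. The documents give no sample inventory for these patients, so smaller counts are assumptions:

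- Scaled by 150/250: n = 120, width 17.9%.
- Scaled by 0.9 × 0.9 × 0.86: n = 139, width 16.6%.
- Scaled by 75% to 80%: n = 150 to 160, width 16.0% to 15.5%.

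**The case against.** A reader might infer that the 85% power and the 14% width are simply not achieved. The documents do not support that.

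- **Power.** At the printed difference of 1.38, 150 patients still give power above 99.9%. The fall to about 62-64% depends on reading the effect size as 0.38. That value fits the stated power and group sizes, but it is an inference. This objection stands.
- **Interval width.** The 14% statement is conditional on 200 patients and is correct at that number. No inventory of progressing dabrafenib/trametinib patients exists in the documents, so 18% is one end of an assumed range. This also stands.
- **Different arms and tube.** The 150 covers Arms A and D and serum for Appendix XVI. Section 11.3 uses heparinized blood. The inventory therefore bears on Aim 2b by analogy and gives no count for Arms B and C. In mitigation, both tubes fall under the same consent and share the baseline, six-weekly, crossover and progression schedule in Section 7.2, and the crossover remark names Arm C as well as Arm D.
- **Uncertain floor.** The 46 is a minimum, the crossover rate was still uncertain, and the 75% to 80% projection is higher. This is why the supportable figure is a range.
- **Missing text.** The opening of the 11.3 statistical text was not available for this check. An allowance for sample loss stated there would change the reading, but it would still have to be squared with counts equal to all treated patients.

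None of this restores 250: the more favourable projection gives at most 200.

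**Conclusion.** The Aim 2b count of 250 is contradicted by the protocol's own later projections, which give about 150 to 200 ipi/nivo patients with samples, a shortfall of 20% to 40%. This assumes that heparin tubes are returned about as often as serum tubes. The two Appendix XVI projections also disagree with each other.

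The consequence for power cannot be stated until 1.38 and 85% are reconciled. If 1.38 is meant, the test is overpowered at any of these counts and 85% is wrong. If 85% at 250 is meant, the difference is about 0.38, and power falls to about 74-76% at 188 to 200 patients and 62-64% at 150.

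For Aims 2a, 2c, 2d and the resistance analyses, a shortfall is plausible but not documented. A worst-case interval width of about 15.5% to 18% follows only if the 200 shrinks to an assumed 120 to 160.

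**What to change.** - Reconcile the two July 2020 projections in Appendix XVI, and correct the printed product so that it yields 104.
- Restate the Aim 2b count, allowing for consent, baseline and week-12 sampling, and crossover. On present figures this is about 150 to 200.
- Reconcile the printed 1.38 with 85% power. State the difference detectable with 85% power: about 0.49-0.50 at 150 patients, about 0.43-0.44 at 188 to 200.
- Restate the counts for Aims 2a, 2c, 2d and the resistance analyses from a heparin-tube inventory that includes Arms B and C, or label them as assumptions. Keep the 14% width only if at least 196 patients are expected; otherwise give the range. The resistance paragraph under Aim 2b repeats the dabrafenib/trametinib counts and should be checked in the same edit.
- Also reconcile the 5% favourable outcome hypothesized in Aim 2b with its 135/115 split, since 135/250 is 54%.

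The cost is wording, a tube count and possibly a less favourable power statement. No patients, samples or procedures change.
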